8 ADVERSE EVENTS

Adverse events will be collected by spontaneous reports from subjects, either verbal or recorded in the subject diary, by directed questioning of subjects, and by observation.

The most common frequently reported adverse reactions during clinical trials with tazarotene cream 0.1% for the treatment of acne were desquamation, dry skin, erythema, and burning sensation, occurring in 10% to 30% of subjects. Adverse reactions occurring in 1% to 5% of treated subjects included pruritus, irritation, face pain, and stinging.

The investigator is to pay special attention at each visit to any signs of clinically significant dryness, non-lesional erythema, and peeling and report as an AE subsequent to the Baseline Visit if worse than at Baseline.

An AE is any untoward medical occurrence in a subject participating in a clinical trial. The event does not necessarily have to have a causal relationship with the study product. An AE can therefore be any sign, symptom, or disease, or any worsening of an existing sign, symptom, or disease, whether or not considered related to the study product or trial procedures, including injuries.

Any medical condition that is present at the time of Screening or Baseline should be considered as medical history and reported on the medical history CRF and should not be reported as an AE except for AEs observed at the Baseline Visit due to study procedures performed at the Screening visit, which should be reported. Anticipated day-to-day fluctuations of pre-existing conditions should not be reported as AEs. Unexpected worsening of pre-existing conditions should be reported as AEs. The disease or condition being studied or expected progression, signs, or symptoms of the disease or condition being studied such as worsening of acne should not be reported as an AE unless it is more severe than expected, results in discontinuation from the study or requires alternative therapy.

All serious adverse events (SAEs), all study product-related events, and all AEs leading to study product discontinuation must be followed until the clinical outcome is determined or until all attempts to determine resolution of the event are exhausted (not recovered is not an acceptable outcome for acute conditions). For other AEs, the status at the last visit can be entered into the CRF.

8.1 Adverse Event Reporting Period

Adverse event data must be collected from the time of signing of Informed Consent until study product treatment is discontinued except for spontaneously reported SAEs, which should be reported up to 30 days after discontinuing study product use and entered into the CRF. Adverse events occurring from the time of the Screening Visit until the Baseline Visit associated with study procedures should also be reported for all subjects, including screen failures.

8.2 Recording Adverse Events

The investigator will record all AEs, regardless of relationship to study product on the AE CRF. Standard medical terminology should be used when describing AEs. Whenever possible a diagnosis should be made and recorded on the CRF rather than listing signs and symptoms. Intermittent AEs can be recorded once. The anatomical location of the AE must be specified when applicable. The following information should be recorded on the CRF:

1. Description, including whether on treated area or not
2. Start date
3. Stop date or date of death, ongoing, or unknown
4. Severity of the event (see Section 8.3.1 Severity for details)
5. Study product use continued or not
6. Outcome of the event (recovered/resolved, recovered/resolved with sequelae, not recovered/not resolved, unknown, fatal)
7. Relationship to study product (see Section 8.3.2 Relationship to Study Product [Causality] for details)
8. Indication of whether the event is serious (see Section 8.3.3 Seriousness for details)
9. Actions taken including treatment with concomitant medication

Laboratory and Vital Signs Variables

Vital signs and laboratory abnormalities (except at the Screening and Day -1 visits and pre-dose on Day 1) should be reported as AEs if they are out of range and considered to be clinically significant, as per the investigator's judgment. If an abnormal laboratory value is associated with clinical signs and symptoms, the sign/symptom should be reported as an AE, and the associated abnormal laboratory result should be considered additional information.

8.3 Assessment of Adverse Events

8.3.1 Severity

It is the investigator's responsibility to assess the severity of each AE. Descriptions of severity are as follows:

1. Mild: Awareness of sign or symptom, but easily tolerated. Not likely to interfere with normal activity or require medical attention.
2. Moderate: Discomfort enough to cause interference with usual activity. May require medical intervention.
3. Severe: Incapacitating such that normal activity is prevented. Likely requires medical intervention and/or close follow-up.

8.3.2 Relationship to Study Product (Causality)

It is the investigator's responsibility to assess the relationship between the study product and the AE. The degree of "relatedness" of the AE to the study product should be described using the following categories:

1. Not Related: The event is clearly due to extraneous causes (e.g., diseases, environment, etc.). Specify if known. Or, the event is most probably produced by other factors such as the subject's clinical state, therapeutic interventions, or concomitant therapy and does not follow a known response pattern to the study product.
2. Possibly Related: The event is temporally related to study product use but can be explained by another etiology. Information on the effect of study product withdrawal may be lacking.

3. Probably Related: The event is temporally related to study product use and is consistent with known effects of the study product and/or improves upon withdrawal of the study product.
4. Definitely Related: The event follows a reasonable temporal sequence from the time of study product administration and/or follows a known response pattern to the study product, and could not have been produced by other factors such as the subject's clinical state, therapeutic intervention, or concomitant therapy, and either occurs immediately following study product administration or improves on stopping the product, or there is a positive reaction at the application site.

8.3.3 *Seriousness*

It is the investigator's responsibility to determine the "seriousness" of an AE. A serious adverse event (SAE) is any AE occurring at any dose that results in any of the following outcomes:

1. Death
2. Life-threatening (subject at immediate risk of death)
3. Inpatient hospitalization or prolongation of hospitalization
4. Results in persistent or significant disability/incapacity
5. Results in congenital anomaly/birth defect

Important medical events that may not result in death, are not life-threatening, or do not require hospitalization may be considered an SAE when, based upon appropriate medical judgment, they may jeopardize the subject and may require medical or surgical intervention to prevent one of the outcomes listed above. Examples of such medical events include allergic bronchospasm requiring intensive treatment in an emergency room or at home, blood dyscrasias or convulsions that do not result in inpatient hospitalization, or the development of drug dependency or drug abuse.

8.4 **Reporting Serious Adverse Events**

SAE information must be faxed or emailed within 24 hours of becoming aware of the event to the Sponsor's medical monitor and appointed Pharmacovigilance person. The minimum *initial* information required to be reported on the Serious Adverse Event Form is: the subject number, subject initials, the event, the causality, the date of the event, and the name of the person reporting the event. This initial report should be promptly followed up with a *completed* Serious Adverse Event Form.

Serious Adverse Events: [name], MS
Associate Director
Clinical Pharmacovigilance, NA
[contact]
Email: [contact]

The initial information must include a causality assessment that is provided by the primary investigator or other medically qualified individual. The causality assessment can be amended as more information is available. Significant new information about ongoing SAEs should be reported promptly to the sponsor.

Serious adverse events will be evaluated by the medical monitor within 24 hours of receipt and plans for management and further reporting (i.e., FDA) determined.

All serious and unexpected suspected SAEs will be reported to the Agency by the Sponsor.

It is the responsibility of the CRO, Symbio LLC, to promptly notify the IRB and other Investigators involved in this study about serious and unexpected SAEs for which there is a reasonable possibility of their being related to the investigational product.

Follow-up of Serious Adverse Events

All follow-up reports will be subject to the same reporting timelines as the Initial Reports. Within 24 hours of receipt of new information, the updated follow-up SAE form, along with any supporting documentation (e.g., patient discharge summary or autopsy reports), should be faxed or emailed to the Sponsor.

8.5 Discontinuation Due to an Adverse Event

The sponsor must be notified within 5 days if any subject is withdrawn or discontinues study product use due to an AE if the event is related to the study product (see title page for contact information).

8.6 Exposure *in utero* (Pregnancy)

If a female subject becomes pregnant during the study, study product must be discontinued immediately and she must be followed through the pregnancy and delivery. The investigator should report the event to the sponsor immediately (see contact information on title page) and complete the Pregnancy Report Form. The expected date of delivery or expected date of the end of the pregnancy should be included in this information. The investigator is instructed to contact the subject every 3 months until the end of her pregnancy and report the outcome to the sponsor. Details of the pregnancy, delivery and health of the infant should be recorded on the Pregnancy Report Form.

The following outcomes of pregnancy fall under the criteria for SAEs and should be reported as such: delivery complications prolonging hospitalization, spontaneous abortion, stillbirth, death of newborn baby, congenital anomaly, and anomaly in a miscarried fetus.

9 DATA HANDLING AND RECORD KEEPING

9.1 Confidentiality

Information about study subjects will be kept confidential and managed according to the requirements of the Health Insurance Portability and Accountability Act. This regulation requires a signed authorization informing the subject of the following:

- What protected health information (PHI) will be collected from subjects in this study
- Who will have access to that information and why
- Who will use or disclose that information
- The rights of a research subject to revoke their authorization for use/disclosure of their PHI.
- Expiration of authorization

If a subject revokes authorization to collect and use PHI, the investigator, by regulation, retains the ability to use all information collected prior to the revocation of authorization. For subjects who have revoked authorization to collect and use PHI, attempts should be made to obtain permission to collect at least vital status (i.e., that the subject is alive) at the end of their scheduled study period.

9.2 Source Documents

Investigators must keep accurate separate records (other than CRFs) of all subject visits that include all pertinent study-related information, including original signed/dated informed consent/ Information and assent forms. Source documents for this study include all written records of study data. All study data must have a paper source document, including investigator assessments.

9.3 Screening/Enrollment Log

A subject Screening/Enrollment Log, noting reasons for screen failure where applicable, must be maintained for all subjects who are consented. The log should also include screening date, subject number, and date of enrollment, which is when ICF is signed, where applicable.

9.4 Case Report Forms

CRFs for individual subjects will be provided by Symbio. CRFs must be legible and complete. CRFs for this study will be maintained in a study binder and data recorded on 2-part NCR paper. One copy will be kept by the investigator and the other copy will be collected by the study monitor. All forms should be completed using a black ballpoint pen. Errors should be lined out, *but not obliterated*, and the correction inserted, initialed, and dated by designated study personnel. Further data corrections will be performed on special “data correction forms” (DCFs) that will be provided to the investigator in case of erroneous or unclear data. The investigator will make the correction on the DCF and sign the DCF. The original will be sent to Symbio and a copy retained with the CRFs.

A CRF must be completed and signed by the investigator for each subject enrolled, including those discontinued from the study for any reason. The reason for discontinuation must be noted on a subject’s study termination form.

CRFs must be kept current to reflect the subject’s status at each phase during the study. Subjects are not to be identified on CRFs by name; appropriately coded identification and the subject’s initials must be used. The investigator must keep a separate log of the subjects’ names and addresses

A Data Management Plan, which describes the programming of database structure, will be prepared.

9.5 Archiving of Study Documentation

The investigator must retain study records for 2 years following the date a marketing application is approved for the investigational product; or, if the application is not filed or is not approved, until 2 years after the investigation is discontinued and the FDA is notified.

The sponsor will inform the investigator, in writing, as to when these documents no longer need to be maintained.

All study documents, original source documents, correspondence, IRB documents, etc. are subject to sponsor and FDA inspection at any time.

10 MONITORING AND DATA QUALITY ASSURANCE

Only persons who are appropriately trained and who have the scientific and clinical knowledge to adequately monitor the study will be selected for monitoring this study. The monitor must have at least 1 year of previous experience in monitoring clinical studies. The monitor should be familiar with the etiology and signs and symptoms of acne and the treatment options that are currently available.

Before study initiation, the investigator and site personnel will receive protocol training from the sponsor's representatives to ensure collection of accurate, consistent, complete, and reliable data. This training will take place either at a web-based Investigator Meeting or individually on-site.

During the study, a monitor will make multiple site visits to check the progress of the study, review consent forms, review protocol compliance, assess drug accountability, and ensure that the study is being conducted according to the protocol and GCP. Any review of the subjects' original medical records will be performed in a manner to ensure that subject confidentiality is maintained. The investigator will ensure that the monitor or other compliance auditor is given access to all study-related documents and has adequate time and space to conduct the monitoring visit including availability of the investigator and site personnel to discuss findings.

Data capture methods will be designed to ensure accurate transfer of data to electronic media.

The sponsor's Quality Assurance representative may conduct QA audits randomly or if needed at 5% to 10% of the investigator sites.

11 STATISTICAL CONSIDERATIONS

All statistical processing will be performed using SAS[®] unless otherwise stated. Two-sided hypothesis testing will be conducted for all inferential analyses using a significance level of 0.05. Efficacy analyses performed using the intent-to-treat (ITT) population will be considered primary. Efficacy analyses performed using the per-protocol (PP) population will be considered supportive. Safety analyses will be performed on the safety population (all subjects who receive study product and provide any post-baseline safety information). Study populations are defined in Section 11.2.

A Statistical Analysis Plan, describing all statistical analyses and outlier testing, will be provided as a separate document prior to database lock and unblinding of the study treatments.

11.1 Sample Size

Approximately 62 subjects will be enrolled in the study. Since the study is not aimed to meet the bioequivalence criteria, proper powering of the study is not required. The sample size chosen for the study attempts adequate representation of pediatric and adult population and was considered adequate to meet the study objectives.

11.2 Analysis Data Sets

11.2.1 Safety Population

All subjects who receive at least one confirmed dose of study product and provide any post-baseline safety information will be included in the safety population. No imputation will be made for missing safety data.

11.2.2 Pharmacokinetic Analysis Population

Samples from all subjects who provide evaluable data will be assayed; these subjects will be included in the PK and statistical analysis. In order to be considered evaluable, a subject must have PK samples collected on both Day 14 and Day 21. An unequal number of subjects per arm will be used.

11.3 Demographic and Baseline Data

Subject demographic and baseline characteristics will be summarized descriptively by treatment group for the safety and PK populations.

11.4 Pharmacokinetic Analyses

Tazarotene and tazarotenic acid plasma concentrations produced by the application of the study products will be determined to establish the PK profile of each treatment regimen. Below limit of quantitation concentrations (coded BLQ) will be treated as zero for all statistical analyses. The PK parameters will be derived from the plasma concentrations versus time profiles. All reported sampling time deviations following application for test and Reference will be taken into consideration for evaluation of PK parameters.

In the case where concentrations of tazarotene and tazarotenic acid cannot be determined due to bioanalytical or clinical reasons, these values will be set to missing for the PK and statistical analysis.

In the case where less than 3 consecutive measurable concentrations of tazarotene and tazarotenic acid are observed, the area under the curve (AUC) parameters will not be estimated for that specific study period.

The following PK parameters will be calculated for tazarotene and tazarotenic acid on Day 14 and Day 21 using a noncompartmental approach. The linear trapezoidal rule will be used to estimate the AUC.

$C_{\max(ss)}$:	Maximum observed maximum plasma concentration during a dosing interval at steady state
$AUC_{0-12(ss)}$	Area under the concentration–time curve from time zero to 12 hours post-dose, at steady state
$AUC_{0-24(ss)}$	Area under the concentration–time curve from time zero to 24 hours post-dose, at steady state
$T_{\max(ss)}$	Time to reach observed maximum plasma concentration, at steady state
$C_{\min(ss)}$	Minimum observed plasma concentration during a dosing interval at steady state

The absorption and disposition parameters will be determined using a noncompartmental approach, the trapezoidal rule will be used to estimate the area under the curve. The PK parameters of interest for this study will be:

Day 14 and Day 21: $T_{\max(ss)}$, $C_{\max(ss)}$, $AUC_{0-12(ss)}$, $AUC_{0-24(ss)}$, $C_{\min(ss)}$,

For Part B, plasma concentration data generated from sparse samples (maximum 4 time points from each subject) on Day 14 and Day 21 will be used for calculation of PK parameters: $C_{\max(ss)}$, $AUC_{(ss)}$, $C_{\min(ss)}$.

Descriptive statistics will be calculated for plasma concentrations at each individual time point and for all PK parameters. The individual plasma concentration/time profiles will be presented using the actual sampling times whereas the mean plasma concentration/time profiles will be presented using the theoretical sampling times. Concentration/time profiles will be presented on linear and semi-log scales.

Pharmacokinetic analyses will be generated using validated PK software (e.g. Phoenix[®] WinNonlin[®] Version 6.3 or higher and Phoenix[®] Connect[™] version 1.3.1 or higher).

A statistical plan will be prepared. Statistical analysis of all PK parameters will be based on a parametric analysis of variance (ANOVA) model. Two-sided 90% confidence intervals of the ratio of geometric least squares (LS) means will be presented from the natural log (ln)-transformed PK parameters ($C_{\max(ss)}$, $AUC_{0-24(ss)}$, $C_{\min(ss)}$) for Treatment 1 vs Treatment 2.

Achievement of steady state will be performed by treatment, using log-transformed $C_{\min(ss)}$ (at Days 12, 13 and 14 and 19, 20 and 21) in a mixed effect model through repeated-measure ANOVA or through other appropriate statistical methods.

Disease severity will be assessed between baseline and sampling days by paired t-test or any other appropriate statistical test and will be presented by treatment.

Descriptive statistics will be presented for safety parameters.

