Subjects will visit the clinical site daily prior to each dose application. Subjects will be confined at the clinic on Day 1 from prior to the evening dose until after that dose, from prior to the evening dose on Day 14 to after the evening dose on Day 14, and from prior to the evening dose on Day 21 to after the 24-hour post dose PK sample collection on Day 22. Subjects will leave the clinic after completion of clinical activities. On Days 14 and 21, blood sampling for PK estimation will be performed over an interval of 24 hours. Adequate trough samples will be collected at the evening visit on Day 1 to assess baseline and on days 12, 13, 14, 19, 20 and 21 to assess attainment of steady state. For the pediatric population in part B, the trough samples will not be collected on days 12, 13, 19 and 20. Any subject missing dosing of any one dose of Reference product and two consecutive doses of Test product between days 1 and 8, or between days 8 and 15 will be considered for steady state estimation at Day 14, or Day 21, respectively. Subject (s) missing either two consecutive dosing days (two doses for reference and four for test product) between day 1 and 8 or missing two non-consecutive dosing days between Day 2 and Day 11 will be assessed for steady-state estimation at Day 21. Subjects missing dosing between Days 12 and 14 and between Days 19 and 21 will not be considered for steady-state estimation or PK and statistical analysis.

For all dosing days (except confinement days), subjects will come to the clinical site ± 1 hour of each dose application (e.g., around 7:00 pm and 7:00 am) for twice-daily application of Test product and (e.g. around 7:00 pm) for once-daily application of Reference product. Subjects will leave the clinical site after completion of the scheduled activities. On Day 14 and Day 21, subjects will report to the clinical site before scheduled dosing, allowing sufficient time for all pre-dosing assessments to be performed.

Blood samples for PK estimation will be collected (within time window ± 15 minutes) at scheduled intervals over a period of 24 hours after the evening dose application for Test product and Reference product on Day 14 and Day 21. On Day 22, for assessment of leave on exposure for 12 hours, the last dose application of Test product (morning dose on Day 22) will not be rinsed off.

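### BLQ values are set to zero for every analysis, yet Cmin(ss) and the steady-state troughs are analysed as logarithms, where zero is undefined and no rule in the supplied text says what happens

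*Combined protocol and SAP*

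**What the plan says.** Section 11.4 gives one rule for low concentrations, with no exception for scale: "Below limit of quantitation concentrations (coded BLQ) will be treated as zero for all statistical analyses".

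It defines Cmin(ss) as "Minimum observed plasma concentration during a dosing interval at steady state". For the comparison of arms it says that two-sided 90% intervals of the "ratio of geometric least squares (LS) means will be presented from the natural log (ln)-transformed PK parameters", these being Cmax(ss), AUC0-24(ss) and Cmin(ss), using a parametric ANOVA. The synopsis plans the same for Day 14 and Day 21.

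For steady state, 11.4 says "Achievement of steady state will be performed by treatment, using log-transformed" Cmin(ss) on Days 12 to 14 and 19 to 21, in a repeated-measures mixed model or some other suitable method that it does not name. Section 4 schedules the troughs "on days 12, 13, 14, 19, 20 and 21 to assess attainment of steady state", but Part B subjects give none on Days 12, 13, 19 and 20.

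Two neighbouring rules in 11.4 look relevant. Concentrations that cannot be determined for bioanalytical or clinical reasons are handled so: "these values will be set to missing for the PK and statistical analysis". The other rule begins "In the case where less than 3 consecutive measurable concentrations of tazarotene and tazarotenic acid are observed" and withholds AUC only. Section 11 defers detail: "A Statistical Analysis Plan, describing all statistical analyses and outlier testing, will be provided as a separate document prior to database lock". That plan is not among the supplied documents.

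**The concern.** A Cmin or trough recorded as zero cannot enter a log-scale model, so the BLQ rule and the analysis rule cannot both be followed. The nearby rules do not help: a BLQ result is not an undeterminable one and has its own rule, and the three-consecutive rule concerns AUC.

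Standard software returns a missing value for the log of zero and drops the record. The records lost are those with the lowest exposure. If the arms lose different shares, the Cmin ratio is distorted; the arms may well differ, because Test is rinsed off after about a minute and Reference stays on for 12 hours (Section 6.2). In the trough check, early low values would be lost first, which flattens a rise that is still under way.

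Comparative bioavailability is the primary objective (Section 3), and Cmin is one of the three parameters for which a ratio is reported.

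**Working it through.** The documents contain no power, effect size, CV, quantitation limit (LLOQ) or BLQ rate, so there is no plan figure to reproduce. BLQ rates, CVs, correlations and true ratios below are assumptions.

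**1. Inputs from the documents.** Part A: 12 vs 12 adults (Section 4) with 11 samples per profile, pre-dose plus 10 (Table 2). Part B: 3 samples (Set 1) or 4 (Set 2) per PK day (Tables 2 and 3).

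**2. How often is the parameter zero?** With BLQ probability p per sample and k independent samples, P(Cmin = 0) = 1 − (1 − p)^k and P(Cmax = 0) = p^k.

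- Part A, p = 0.10: Cmin 1 − 0.9^11 = 69%; Cmax about 0. With within-subject correlation 0.5 and 0.9 (simulated), Cmin falls to 42% and 21%, and Cmax rises to 0.1% and 3%. Independence is thus an upper bound for Cmin.
- Part A, p = 0.20, correlation 0 / 0.5 / 0.9: Cmin 91 / 63 / 36%; Cmax 0 / 0.7 / 8%.
- Part B, independent, p = 0.10: Cmin 1 − 0.9^3 = 27% or 1 − 0.9^4 = 34%.
- Part B, independent, Cmax: at p = 0.20, 0.2^3 = 0.8% or 0.2^4 = 0.2%; at p = 0.50, 12.5% or 6%.

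**3. Effect of dropping on the ratio (12 vs 12, CV 60% in both arms, true ratio 0.50).** σ = √ln(1 + 0.6²) = 0.5545. A ln-normal arm with mean μ, kept only above L = ln(LLOQ), has mean μ + σ·φ(z)/(1 − Φ(z)), where z = (L − μ)/σ. Set μ = ln 0.50 for Test and 0 for Reference, and choose L to give the stated Test share.

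| Test BLQ | Test shift | Reference BLQ | Reference shift | Estimated ratio | 90% CI coverage |
|---|---|---|---|---|---|
| 10% | 0.108 | 0.6% | 0.009 | 0.55 | 87% |
| 25% | 0.235 | 2.7% | 0.036 | 0.61 | 77% |
| 50% | 0.442 | 10.6% | 0.113 | 0.695 | 59% |

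The ratio is exp(ln 0.50 + Test shift − Reference shift); for 25%, exp(−0.693 + 0.235 − 0.036) = 0.61. Coverage comes from 20,000 simulated trials with a pooled-variance t interval.

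At a true ratio of 0.80 the estimates are 0.84, 0.88 and 0.91 (coverage 89, 87 and 83%). At 1.0 the two shifts cancel: no bias, coverage 90%.

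**4. Direction.** With unequal CVs the cancellation fails. Take Test 60%, Reference 40% (σ = 0.385), true ratio 1.0 and 20% of Reference BLQ. The Test shift is 0.259 and the Reference shift 0.135, so the ratio is exp(0.124) = 1.13 (coverage 82%). With the CVs exchanged and 20% of Test BLQ it is 0.88 (82%).

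**5. Troughs (Part A; 12 subjects, 3 days, ln-SD 0.5 between and 0.3 within).** A true rise of 20% per day is estimated as about 14% and 11% when 25% and 50% of troughs are BLQ and dropped. Power to detect it falls from about 81% to 41–48% and 24–29%, depending on how the model is fitted. With no true rise there is no bias.

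**6. The remedy under the step 3 assumptions.** A censored-normal fit gives 0.500 (coverage 90%) at 25% BLQ and 0.505 (91%) at 50%. LLOQ/2 substitution gives about 0.46 (88%) at both.

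**The case against.** The best reply is that handling of zeros belongs in the separate statistical plan, which we have not seen. That plan may well deal with it. But 11.4 is not silent: it prescribes zero for all statistical analyses. A plan that obeys it fails on the log scale, and one that does otherwise departs from the protocol.

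For troughs, the allowance for another suitable method means the mixed model is not the only route. This weakens the trough point without answering it, since no method or BLQ rule is named and the allowance does not extend to the Cmin ratio.

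It is also fair that BLQ values may be rare: at 10% of Test BLQ and a true ratio of 0.80, dropping gives 0.84 with 89% coverage, which is negligible. Section 11.1 disclaims a bioequivalence aim, so no pass/fail decision turns on Cmin. And a simple stated substitution would close the gap; the censored model is the better performer here, not the only acceptable answer.

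A reader might infer more than the text supports:

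- **That the plan deletes low exposures.** It does not say so; deletion is the software default.
- **That Cmax is compromised alongside Cmin.** It needs a wholly BLQ profile, which is rare with 11 samples and more possible with 3 or 4.
- **That the ratio always moves toward 1.** Step 4 shows otherwise when variability differs.

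**Conclusion.** The conflict within 11.4 is real and can be read off the text: zero for all analyses cannot coexist with logged Cmin and logged troughs. It chiefly affects the Cmin(ss) ratio in both parts and the trough check in Part A; Cmax is a minor concern, mainly in Part B. It applies to each analyte.

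Its size in this trial is unknown. The calculations show that default dropping can be harmless (equal exposure and equal CVs, or few BLQ values) or serious: a true 0.50 reported as 0.61 to 0.70 with coverage of 77 to 59% when 25 to 50% of Test is BLQ. These rest on lognormal data, a simple two-sample interval in place of an ANOVA whose terms are not given, 12 per arm, and assumed BLQ rates. Bias in the Part B ratio has not been quantified.

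The risk is a misreported Cmin ratio and a steady-state statement that is too favourable, not a wrong regulatory pass or fail. It should be fixed before database lock. Section 7.5 says Part A PK has been assessed, so the sponsor can count BLQ values now and learn how much this matters.

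**What to change.** In 11.4, and in the separate statistical plan:

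1. Limit BLQ = 0 to descriptive concentration summaries and the linear trapezoid.
2. For ln-scale Cmin(ss), log-scale troughs, and Cmax(ss) where a whole profile is BLQ, treat the value as left-censored at ln(LLOQ) in a censored-normal model with the same terms (including the subject effect for troughs).
3. Add LLOQ/2 substitution as a sensitivity analysis.
4. Where an arm has fewer than 3 measurable values for a parameter and day, report BLQ counts and descriptive results without a ratio.
5. Report BLQ counts by arm, analyte and day.

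Because Part A has been assessed, date the change.

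The cost is wording and some programming; no new data are needed. The censored model leans on the lognormal tail. Its intervals are wider than those after dropping: ln-width 0.80 against 0.67 at equal exposure with 25% BLQ in both arms. But 0.67 is falsely narrow, since complete data would give about 2 × 1.717 × 0.5545 × √(2/12) = 0.78.

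Heavy censoring remains a limit. With 12 per arm, the chance of fewer than 3 measurable values is (1 + 12 + 66)/4096 = 2% at 50% BLQ, 25% at 70% and 56% at 80%. At 80% of Test BLQ and a true ratio of 0.50, trials that still yield a ratio have coverage of only about 83%.
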